### SAE Reporting

The investigator should report all SAEs to the Sponsor as soon as possible but no later than outlined below.

Clinical Site	Reporting timelines
All Sites	SAEs must be reported to the Sponsor no later than 3 calendar days from the day the site personnel became aware of the event or as per the investigative site's local requirements, if the requirement is more stringent than those outlined above.

The date the site staff became aware the event met the criteria of an SAE must be recorded in the source document. The Investigator will further report the SAE to the local IRB/EC according to the institution's IRB/EC reporting requirements.

### **7.3.2 Unanticipated Serious Adverse Device Effect Reporting to Sponsor and IRB**

The Sponsor requires the Investigator to report any USADE to the Sponsor within 3 calendar days of the investigator's knowledge of the event, unless local requirements are more stringent, and to the IRB/EC per IRB/EC requirements.

### **7.3.3 Device Deficiency Reporting**

All device deficiencies should be reported on the appropriate CRF form.

## Clinical Investigation Plan

The investigator should report all device deficiencies to the Sponsor as soon as possible but no later than outlined below.

Clinical Sites	Reporting timelines
All Sites	Device deficiencies must be reported to the Sponsor no later than 3 calendar days from the day the site personnel became aware of the event or as per the investigative site's local requirements, if the requirement is more stringent than those outlined above.

The device, if not implanted or not remaining in the subject, should be returned to the Sponsor.

Device deficiencies should be reported to the IRB/EC per the investigative site's local requirements.

An offline form will be made available to allow the investigator to report device deficiencies in the event that the entry cannot be made in the EDC system. This does not replace the EDC reporting system. All information must still be entered in the EDC system as soon as feasible.

In case a device deficiency occurred before the patient ID has been assigned, the device deficiency should be reported to the Sponsor via the offline reporting form.

### 7.3.4 Adverse Event Reporting to Country Regulatory Authorities by the Sponsor

The Sponsor will report SAEs and reportable device deficiencies to the country regulatory authority per local requirements.

Note: Reportable device deficiencies include device deficiencies that might have led to an SAE if a) suitable action had not been taken or b) intervention had not been made or c) if circumstances had been less fortunate. These are handled under the SAE reporting system.

## 8 STATISTICAL CONSIDERATIONS

The following section describes the statistical methods for the clinical study. Additional details on statistical analyses, including justification of clinical study design, poolability analyses, subgroup analysis, and analysis of descriptive endpoints will be maintained in a separate Statistical Analysis Plan (SAP).

### 8.1 Analysis Population

The analysis population will include all subjects in whom a Navitor implant is attempted, excluding roll-in cases. A Navitor implant attempt is defined as insertion of the FlexNav Delivery System (loaded with a Navitor Valve) into the subject's vasculature.

### 8.2 Statistical Analyses

#### 8.2.1 Primary Safety Endpoint Analysis (Portico NG cohort)

The primary safety endpoint for the Portico NG cohort is all-cause mortality at 30 days post index procedure.

The proportion of Portico NG subjects experiencing a primary safety endpoint will be estimated from the binomial model. The 95% confidence intervals will be calculated using the exact Clopper–Pearson method. The estimated primary safety endpoint rate at 30 days will be descriptively compared with the all-cause mortality rates (and 95% confidence intervals) of FDA approved TAVR devices studied in the same

### Clinical Investigation Plan

patient population (e.g., high and extreme risk), [REDACTED], and additional published data on high and extreme surgical risk subjects available at the time of PMA submission.

[REDACTED]

[REDACTED]	[REDACTED]	[REDACTED]
[REDACTED]	[REDACTED]	[REDACTED]
[REDACTED]	[REDACTED]	[REDACTED]
[REDACTED]	[REDACTED]	[REDACTED]
[REDACTED]	[REDACTED]	[REDACTED]

The analysis population will include subjects who undergo a Navitor implant attempt that is described in Section 8.1.

#### 8.2.2 Primary Safety Endpoint Analysis (Titan cohort)

The primary safety endpoint for the Titan cohort is all-cause mortality at 30 days post index procedure.

The proportion of Titan subjects experiencing a primary safety endpoint will be estimated from the binomial model. The 95% confidence intervals will be calculated using the exact Clopper–Pearson method. The estimated primary safety endpoint rate at 30 days will be descriptively compared with the all-cause mortality rates (and 95% confidence intervals) of FDA approved large valve TAVR devices studied in the same patient population (e.g., high and extreme risk) as well as results from the Portico NG cohort.

The analysis population will include subjects who undergo a Navitor Titan implant attempt that is described in Section 8.1.

[REDACTED]

## Clinical Investigation Plan

[figure not shown]
### 8.2.3 Primary Effectiveness Endpoint Analysis (Portico NG cohort)

The primary effectiveness endpoint for the Portico NG cohort is moderate or greater paravalvular leak at 30 days.

[figure not shown]
Let  $\pi$  be the proportion of Portico NG subjects who experience a primary effectiveness endpoint event at 30 days. The following hypothesis will be tested:

[figure not shown]

$$H_0: \pi \geq 8.5\%$$

$$H_a: \pi < 8.5\%$$

$\pi$  will be estimated as a binomial proportion. The hypothesis will be tested at the 0.05 significance level and the null hypothesis will be rejected if the 95% upper confidence bound (UCB) for the proportion,  $\pi$ , is less than the performance goal of 8.5%. 

The results for the primary effectiveness endpoint will be considered successful if the null hypothesis is rejected.

## Clinical Investigation Plan

The analysis population will include subjects who undergo a Navitor implant attempt that is described in Section 8.1 and who have 30-day paravalvular leak status as determined by the echocardiography core laboratory.

### 8.2.4 Primary Effectiveness Endpoint Analysis (Titan cohort)

The primary effectiveness endpoint for the Titan cohort is moderate or greater PVL at 30 days post index procedure.

The proportion of Titan subjects experiencing a primary effectiveness endpoint will be estimated from the binomial model. The 95% confidence intervals will be calculated using the exact Clopper–Pearson method. The estimated primary effectiveness endpoint rate at 30 days will be descriptively compared with 30-day moderate or greater PVL rates (and 95% confidence intervals) of FDA approved large valve TAVR devices studied in the same patient population (e.g., high and extreme risk) as well as results from the Portico NG cohort.

[figure not shown]
[figure not shown]
[figure not shown]
[figure not shown]
[figure not shown]

[figure not shown]

The analysis population will include subjects who undergo a Navitor Titan implant attempt that is described in Section 8.1 and who have 30-day paravalvular leak status as determined by the echocardiography core laboratory.

### 8.2.5 Secondary Endpoint Analysis

The secondary endpoint is a non-hierarchical composite of all-cause mortality, disabling stroke, life threatening bleeding, acute kidney injury (stage 3), or major vascular complications at 30 days. This endpoint will be analyzed for both the Portico NG and Titan cohorts separately.

The proportion of subjects experiencing a secondary endpoint will be estimated from the binomial model. The 95% confidence intervals will be calculated using the exact Clopper–Pearson method. The estimated secondary endpoint rate at 30 days will be descriptively compared with rates observed with FDA approved TAVR devices studied in the same patient population (e.g., high and extreme risk), including the observed rates and 95% confidence intervals from published sources shown in Table 8 below and data from FDA approved devices available at the time of PMA submission.

### Clinical Investigation Plan

[figure not shown]
## Clinical Investigation Plan

### 8.3 Sample Size Calculation and Assumptions

The total sample size required for the Portico NG cohort (to ensure adequate number of subjects for analysis of the primary endpoints) is 169 subjects as described in more detail below.

For the Titan cohort, a total of 60 analysis provides an adequate sample size to descriptively compare to results from competitor studies of a larger valve size (e.g., Evolut R 34mm) and the Portico NG cohort.

### 8.4 Timing of Analysis

The analysis for the PMA submission will be conducted on a dataset locked after a minimum of 152 analysis subjects in the Portico NG cohort have had a 30-day study visit and have PVL data assessed by the echocardiography core laboratory. As stated in section 3, an analysis of the first 80 subjects (with a Navitor implant attempt) with 30-day follow-up data will be provided to support the CE Mark submission.

Data from the Titan cohort will be analyzed independently from the Portico NG cohort. The analysis for the Titan cohort will be conducted on a dataset locked after 60 analysis subjects have had a 30-day study visit and have PVL data assessed by the echocardiography core laboratory, excluding any subjects who die or are lost to follow-up within 30 days.

### 8.5 Subgroup Analysis

No subgroup analyses are planned for this clinical study.

### 8.6 Multiplicity

The clinical study has two (2) co-primary endpoints with hypothesis testing only for the primary effectiveness endpoint in the Portico NG cohort. Therefore, there is no multiplicity adjustment planned in this clinical study.

### 8.7 Pooling Strategy

Additional information regarding the planned pooling strategy in this clinical study will be maintained in a separate Statistical Analysis Plan (SAP).

### 8.8 Procedures for Accounting for Missing Data

There is no plan to impute missing data for this clinical study.

## Clinical Investigation Plan

### 8.9 Planned Interim Analysis

No interim analyses are planned for this clinical study.

### 8.10 Statistical Criteria for Termination

There are no statistical criteria for termination of this clinical study.

### 8.11 Success Criteria

Study success will be determined independently for the Portico NG and Titan cohorts. The Portico NG cohort will be considered successful if the rate for the primary safety endpoint (all-cause mortality within 30 days) is within expected ranges as compared to previous commercially approved devices studied in the same patient population (e.g., high and extreme surgical risk) and the null hypothesis is rejected for the primary effectiveness endpoint (moderate or greater PVL at 30 days).

The Titan cohort will be considered successful if three (3) or fewer deaths occur within 30 days of the index procedure in 60 analysis subjects.

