# Clinical Investigation Plan

## 1 INTRODUCTION

This document is a clinical investigational plan (CIP) for a prospective, multi-center, international, single-arm investigational study intended to support regulatory approvals of the Portico™ NG Transcatheter Aortic Heart Valve (Portico NG, to be named Navitor™ upon commercialization) used in combination with the FlexNav™ Delivery System. As of protocol revision D, this study includes a product size extension (Navitor Titan™ valve) analyzed as a separate cohort. When the product is referenced as the Navitor Valve in this document, this language applies to both the Navitor 23-29mm valve sizes and Navitor Titan Valve. The investigational devices are intended for use in patients with symptomatic severe native aortic stenosis, who are considered high or extreme surgical risk. This clinical study is sponsored by Abbott.

The primary objective of the clinical study is to evaluate the acute safety and effectiveness of the Navitor Transcatheter Aortic Heart Valve based on the rates of all-cause mortality at 30 days and moderate or greater paravalvular leak at 30 days.

This clinical study will be conducted in accordance with this CIP. All investigators involved in the conduct of the clinical study will be qualified by education, training, or experience to perform their tasks and this training will be documented appropriately.

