### 4 ENDPOINTS

#### 4.1 Primary Endpoints and Rationale

This clinical study has two (2) co-primary endpoints. The same primary endpoints will be evaluated in both the Portico NG and Titan cohorts and analyzed independently for each cohort.

The primary safety endpoint is all-cause mortality at 30 days. The 30-day primary safety endpoint is established by VARC-2 as the most appropriate time period to assess the safety of the procedure. It is also consistent with the primary safety endpoint used in the Portico TAVI System CE Mark Study (NCT01493284) and is consistent with the timepoint of assessment of the primary safety endpoint for multiple pivotal TAVR trials.

The primary effectiveness endpoint is moderate or greater paravalvular leak at 30 days. The primary effectiveness endpoint will characterize the ability of the new fabric outer cuff that has been added to the exterior portion of the valve stent to optimize valve sealing and minimize paravalvular leak (PVL). Moderate or greater PVL was selected as the primary effectiveness endpoint based on the clinical relevance and associated link to increased risk of mortality. Hermann et al. reported that moderate or greater PVL was associated with a statistically significant increase in the risk of mortality at 1 year as compared to none/trace (HR: 3.65,  $p < 0.01$ ) or mild PVL (HR: 3.29,  $p < 0.01$ ), thus supporting the relevance of moderate or greater PVL as the primary effectiveness endpoint. For additional details on the primary endpoints including analysis and success criteria, please refer to section 8.2 (Statistical Analyses).

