## Statistical Analysis Plan

infectious disease for the trial primary and secondary endpoints set forth in assessing the trial success and labeling claims. In alignment with the guidance document “FDA Guidance on Conduct of Clinical Trials of Medical Products during COVID-19 Public Health Emergency” updated on 03-June-2020, additional consideration was given to the impact of the COVID-19 pandemic on the primary endpoint analyses for this study. As such, prespecified methods are included in the sections that follow to indicate the handling of any outcomes impacted by COVID-19 as well as efforts to minimize missing endpoint data during the COVID-19 pandemic. Specific analyses to address COVID-19 impacts are included in relevant subsections in Section 2.3.

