##### 2.3.1.2 Primary Safety Endpoint (Titan cohort)

The primary safety endpoint for the Titan cohort is all-cause mortality at 30 days post index procedure.

The proportion of Titan subjects experiencing a primary safety endpoint will be estimated from the binomial model. COVID-19 relatedness of mortality will be adjudicated by the Clinical Events Committee (CEC), and any 30-day death that is adjudicated as COVID-19 related will be excluded from the primary analysis (i.e., from both numerator and denominator). The 95% confidence intervals will be calculated using the exact Clopper-Pearson method. The estimated primary safety endpoint rate at 30 days will be descriptively compared with the all-cause mortality rates (and 95% confidence intervals) of FDA approved large valve TAVR devices studied in the same patient population (e.g., high and extreme risk) as well as results from the Portico NG cohort.

The analysis population will include subjects who undergo a Navitor Titan implant attempt that is described in Section 2.1.1, including subjects who withdraw or are lost to follow-up prior to 30-day visit.

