### 2.13 Sensitivity Analysis

For the primary safety endpoint, a sensitivity analysis will be conducted including all CEC adjudicated death events regardless relationship to COVID-19 to assess the impact of the pandemic. Sensitivity analysis will also be conducted including all CEC adjudicated VARC-2 events regardless to COVID-19 to assess the impact of the pandemic. Sensitivity analysis on the primary endpoint and the VARC-2 event rate will be performed for both the Portico NG and Titan cohorts independently.

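### Titan success: the protocol and SAP count COVID-19 deaths differently, the co-primary PVL endpoint cannot affect the verdict, and the 60-subject lock has little visible room for missing PVL readings

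*Protocol*

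**What the plan says.** **Success rule.** Under protocol 8.11, Titan is "considered successful if three (3) or fewer deaths occur within 30 days of the index procedure in 60 analysis subjects". The analysis population is defined by implant attempt: "The analysis population will include all subjects in whom a Navitor implant is attempted, excluding roll-in cases" (protocol 8.1). Protocol 5.6 plans 60 attempted Titan implants. The Titan success sentence in SAP 2.7 also refers only to deaths, but part of it is redacted.

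**COVID-19 deaths.** Protocol 8.2.2 and 8.11 contain no COVID-19 exclusion. SAP 2.3.1.2 says for Titan that "any 30-day death that is adjudicated as COVID-19 related will be excluded from the primary analysis (i.e., from both numerator and denominator". SAP 2.2.4 describes the purpose of this handling as limiting confounding from the "infectious disease for the trial primary and secondary endpoints set forth in assessing the trial success and labeling claims". SAP 2.13 adds that "a sensitivity analysis will be conducted including all CEC adjudicated death events regardless relationship to COVID-19", for both cohorts.

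**Role of PVL.** Protocol 4.1 and SAP 1.4 name two co-primary endpoints, 30-day mortality and 30-day moderate or greater PVL, and state: "The same primary endpoints will be evaluated in both the Portico NG and Titan cohorts and analyzed independently for each cohort". The objective in protocol 2.1.1 names both endpoints for the Navitor valve, and protocol 1 says of that name that "this language applies to both the Navitor 23-29mm valve sizes and Navitor Titan Valve". For Titan, however, protocol 8.2.4 provides only that "The estimated primary effectiveness endpoint rate at 30 days will be descriptively compared with 30-day moderate or greater PVL rates".

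**Lock.** Protocol 8.4 and SAP 2.6 lock the Titan data once 60 analysis subjects have a 30-day visit and a core-laboratory PVL assessment, with subjects who die or are lost to follow-up within 30 days excepted. For Portico NG, the protocol plans 169 attempts and locks at a minimum of 152 subjects with PVL data.

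**The concern.** Each rule is readable alone, but the three do not fit together.

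1. The protocol's success rule and the SAP's primary safety analysis can give opposite verdicts on the same deaths. In a single-arm cohort whose verdict is a simple count, which deaths count should be settled before the data are seen.
2. A reader told that mortality and PVL are co-primary may take a Titan success to cover both, when only mortality was judged.
3. The lock may not be reachable with the planned number of attempts. The team would then have to decide late whether to lock short, add subjects or wait.

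**Working it through.** **The plan's own figure.** The limit is 3/60 = 5.0% (exact 95% CI 1.04 to 13.92%). No reference rate, error rate or margin behind it is visible, and parts of protocol 8.2.2 and SAP 2.7 are redacted. It therefore cannot be re-derived as a design figure, and the absence of a rationale is not held against the plan.

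**1. Death count.** Take four deaths, one adjudicated COVID-19 related.

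| Count | Deaths/N | Rate | Exact 95% CI | Against a limit of 3 |
|---|---|---|---|---|
| Protocol 8.11, all deaths | 4/60 | 6.7% | 1.85 to 16.20% | fails |
| SAP 2.3.1.2, COVID-19 excluded | (4−1)/(60−1) = 3/59 | 5.1% | 1.06 to 14.15% | within |

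The SAP count also leaves 59 subjects for a rule written for 60.

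One exclusion decides the verdict when there are exactly four deaths. P(X = 4) = C(60,4) p⁴(1−p)⁵⁶, using 30-day mortality rates quoted in protocol 1.1.1:

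| p | P(exactly 4 of 60) |
|---|---|
| 1.4% | 0.9% |
| 2.2% | 3.3% |
| 4.2% | 13.7% |

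These are ceilings for the one-death flip, since at least one of the four deaths must also be COVID-19 related and the documents give no such share. If each death had an assumed, independent 10% chance of being COVID-19 related, the factor would be 1 − 0.9⁴ = 0.344, giving about 0.3%, 1.1% and 4.7%.

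**2. PVL in the verdict.** The Titan rule contains no PVL term, so no PVL count alters it. As illustrations rather than forecasts, with three or fewer deaths Titan succeeds at 6/60 with moderate or greater PVL (10%, CI 3.8 to 20.5%) and at 12/60 (20%, CI 10.8 to 32.3%). Portico NG must also reject a PVL rate of 8.5% or more. At 152 subjects that allows at most 7 events (4.6%): the one-sided exact 95% bound is 8.48% at 7 and 9.30% at 8. The exact method is my assumption, because the method for that bound is not visible.

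**3. Lock.** The exception for deaths and losses can be read in two ways.

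- *These subjects fall outside the 60.* Then 60 attempts cannot yield 60 qualifying subjects once one death or loss occurs.
- *They are excused within the 60.* Then every other subject needs a reading, with no visible allowance for a missed or persistently unreadable echocardiogram. At an assumed independent 1% or 2% chance of a missing reading per subject, the chance of at least one in 60 is 1 − 0.99⁶⁰ = 45% or 1 − 0.98⁶⁰ = 70%.

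Portico NG has an allowance of 169 − 152 = 17 attempts (17/169 = 10.1%), which must also absorb deaths and losses. The same ratio applied to Titan gives 60 × 152/169 ≈ 54 readings.

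**The case against.** **The SAP ranks its own counts.** SAP 2.3.1.2 makes the COVID-excluded count primary and SAP 2.13 makes all deaths a sensitivity analysis. A reader might infer that nothing ranks them, which goes too far. What stands is the mismatch with protocol 8.11, which the visible text of SAP 2.7 does not resolve. The redacted words there might qualify the deaths counted.

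**Adjudication is independent.** A reader might infer that the sponsor could relabel deaths to reach success. The documents do not support that, because the Clinical Events Committee decides relatedness. The open question is which count applies.

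**Descriptive PVL is a disclosed choice.** Protocol 8.2.4, 8.6 and 8.11 are open about it, PVL is still reported with exact intervals, and protocol 4.1 promises only evaluation and analysis. This stands, so the defect is in the label and not in the absence of a test.

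**The lock is less rigid than it looks.** A reader might infer that it tolerates no missing reading, or set 17 of 169 against 0 of 60. Neither holds: deaths and losses are excepted, and the Portico NG 17 includes them. Unreadable examinations must be repeated (protocol 6.6), and subjects from a separate regional protocol outside the US (OUS) may be combined to reach what protocol 3 calls a minimum. The PVL analysis itself is restricted to subjects with a reading, so fewer than 60 can be analysed.

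Nor does a visit at a non-study site necessarily lack PVL. Protocol 6.5.2 limits such visits to standard-of-care data and protocol 15.4 places scheduled follow-up echocardiograms outside standard of care, but local practice may still include one. These points soften the third part without removing it.

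**Conclusion.** The concern holds in three parts of unequal strength.

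- **Strongest:** the protocol and SAP disagree on which deaths count toward Titan success, and one COVID-19 death can reverse the verdict (4/60 against 3/59). The chance is at most 0.9% to 13.7% over mortality of 1.4% to 4.2%, and lower by an unknown factor. That the SAP exclusion reaches the success rule is inferred from SAP 2.2.4 and 2.3.1.2, and the redaction in SAP 2.7 limits certainty.
- **Clear but a matter of labelling:** PVL is co-primary for Titan in name and has no part in its success rule.
- **Weakest:** under either reading of the lock, 60 attempts leave a gap, for deaths and losses under one and for other missing readings under the other. How often it would matter depends on missing-data rates that the documents do not give.

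This should be corrected. It does not invalidate the Titan analyses.

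**What to change.** 1. **Death count.** In protocol 8.11 and SAP 2.7, 2.3.1.2 and 2.13, state that the limit of three applies to all deaths among the 60 attempted Titan subjects, including any combined OUS subjects. Fix the 60 before outcomes are reviewed, for example by consecutive procedure date while keeping the minimum of 30 US subjects in protocol 3. Report the COVID-excluded rate alongside. Reconcile the same mismatch for Portico NG (protocol 8.2.1, SAP 2.3.1.1), so that the cohorts do not differ by accident.
2. **PVL.** In protocol 4.1 and 8.11 and SAP 1.4 and 2.7, state that Titan success is a safety-only verdict and that PVL is reported descriptively and does not enter it.
3. **Lock.** In protocol 8.4 and SAP 2.6, lock when all 60 attempted subjects have completed the 30-day visit, died or exited, and all submitted 30-day echocardiograms have been read. Report the number without a PVL reading.

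**Cost.** No added subjects. The death count is slightly stricter than the SAP's, and the Titan claim is narrower. The lock no longer guarantees a minimum number of PVL readings. At 54 readings, the upper exact 95% limit for 2 events is 12.7%, against 11.5% at 60.
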